A block randomization will be used to assign patients to either the SHGNB or to the sham procedure group. Randomization will be performed using a randomization program and the results placed in independent envelopes. These envelopes will be opened based on order of inclusion into the study and will determine the group in which patients will be placed.

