7.1. Study Design and procedures

This is a double-blinded prospective randomized clinical study. All procedures will be performed by experienced interventional radiologists in the two MUHC study centers: Royal Victoria Hospital and Montreal General Hospital. Other Canadian hospital centers have shown interest in this protocol and may be added to the study at later dates.

Upon referral to the angiography department for a UAE, the radiologist will assess the patient to determine if she is eligible for recruitment into the study based on the inclusion and exclusion criteria (see Appendix I). This will be performed at the time of a consultation, which occurs up to three months before the actual procedure. If the patient is eligible, she will be explained the study and provided with an information sheet. She will be allowed to decide immediately whether she wants to participate or will be allowed to think about it and left to decide on the day of the procedure. An informed consent will be signed. The visual analogue scale will be explained as well as the commitment to complete the data sheets and return them, or to use the web service.

On the day of the procedure, a randomization envelope will be opened and the person will be assigned to either the sham procedure group or to the SHGNB group.

For both groups the UAE procedure itself will be identical. During the UAE procedure the patient will be offered IV sedation at the start to the amount of 1 mg of midazolam and 50 ug of fentanyl. Further additional doses will be upon request from the patient only. The patient will be informed to ask for more if she needs it. Prior to giving another dose, the patient will be asked to rank their discomfort on a scale of 0-10.

The UAE procedure consists of embolization of both uterine arteries. The SHGNB is usually performed in between embolization of both sides. Therefore for the SHGNB group, the block will be performed after the left uterine artery has been embolized. Following the block, the right uterine artery will be embolized. Similarly the sham procedure will also be performed at the time between both embolization.

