7.4 Day of the UAE procedure

If consent had not been obtained at the day of the consult because the patient wanted to think about it some more, the patient could be asked at this time whether they want to participate in the study or not. If this is the case, all discussion will occur outside of the angiography room and the patient given information sheet and will be given time to decide whether they would like to participate or not.

If they have decided to participate, a pre-randomized envelope will be opened and will decide whether the patient gets the hypogastric block or the sham procedure. UAE will proceed as per usual. The patient will be recovered for at least 4 hours in the recovery room. Data regarding pain management while in the recovery room will be gathered on the provided information sheets (see appendix). Before discharge, the patient will be seen by one of the interventional radiologists to complete a visual analog pain scale and collect the information that has been gathered. The patient will be provided an anonymization number and reminded to fill out the pain forms at home via hard copy that

she can bring back to us at the time of the follow-up or mail to us (see appendix), or that she can fill out anonymously by internet.

Procedural information will be collected and stored in a secure area for future analysis.

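### Randomization is not stated to be stratified by hospital and the analysis names no hospital term, so balance between arms within each hospital is left to chance; a minor gap, cheap to close

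*Combined protocol and SAP*

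**What the plan says.** Section 6.3 (Randomization) is short. It says "A block randomization will be used to assign patients to either the SHGNB or to the sham procedure group", that a program generates the allocations, that they go into envelopes, and that "These envelopes will be opened based on order of inclusion into the study". It gives no block size and no stratification factor. It does not say whether there is one envelope series or one per hospital, or which event counts as inclusion.

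Section 7.1 places the trial "in the two MUHC study centers: Royal Victoria Hospital and Montreal General Hospital" and adds: "Other Canadian hospital centers have shown interest in this protocol and may be added to the study at later dates".

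On timing, section 7.1 says of the eligibility assessment: "This will be performed at the time of a consultation, which occurs up to three months before the actual procedure". Allocation comes later: "On the day of the procedure, a randomization envelope will be opened". Table 1 marks randomization on the procedure day only, and section 7.4 agrees. Appendix II holds the envelope closed until the operators change over, and Appendix I enters the envelope number in the ID code at the time of the block. That ID code also records the hospital.

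The analysis is described in the synopsis (Statistical Methods), section 5 and section 8. It consists of chi-square tests, t-tests, regression of pain over time, and ANOVA or multivariate logistic regression for the interplay of several variables. Hospital is not named as a term in any of them.

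**The concern.** The outcomes are self-rated pain and analgesic use. Both could vary with the recovery-room team, the operators and the discharge prescriptions, and so with the hospital. Permuted blocks force balance along the list on which they are built. If patients from two hospitals draw from one list, each hospital receives an arbitrary part of every block, and nothing forces its own patients to be split evenly between block and sham.

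In a 50-patient trial, chance imbalance by hospital adds avoidable noise to the treatment comparison. In proportional terms the imbalance is larger at the 20-patient look, where a significant result ends the trial. The plan controls hospital neither in the stated design nor in the stated analysis. Leaving inclusion undefined adds a smaller problem: two sites could apply the envelope rule differently.

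**Working it through.** **Inputs from the protocol.** Total 50, 25 per group; difference 2 points (7 to 5); SD 2.5; two-tailed 0.05 (section 8); interim look at 20 patients; two hospitals.

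**Assumptions not in the protocol.** One shared envelope series; block size 4, 6 or 10; hospital split 50:50 or 30:70; a hospital difference of D points in pain, with D = 1 as the working value.

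**The plan's own figures.** Effect size = 2/2.5 = 0.8, as stated. The total of 42 is reproduced by a t-test with one-sided alpha 0.05; the two-sided t-test needs 52. That is a separate matter. Because section 8 is two-tailed, the baseline here is two-sided power at 25 per group, which is 79.1%.

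**Imbalance within a hospital at N = 50 (20,000 simulated trials per setting).**

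| Measure | Shared series | Separate series per hospital |
|---|---|---|
| Mean arm difference at a hospital | about 2.5 to 2.9 patients | about 0.7 to 1.1 patients |
| Arm difference of 5 or more, 50:50 split | about 20% to 21% | about 0.1% or less |
| Arm difference of 5 or more, hospital with a 30% share | about 16% to 18% | about 0.1% or less |
| Arm difference of 7 or more, 50:50 split | about 6% to 7% | not tabulated |

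The overall arm difference at N = 50 averages under 1 patient with a shared series, so overall balance is kept.

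**Between-arm difference in hospital share.** With n per arm and share p at one hospital, SD = sqrt(p(1 − p) × 2/n).
- N = 50, p = 0.5: sqrt(0.25 × 2/25) = 0.141.
- N = 50, p = 0.3: sqrt(0.21 × 2/25) = 0.130.
- N = 20, p = 0.5: sqrt(0.25 × 2/10) = 0.224.
- N = 20, p = 0.3: sqrt(0.21 × 2/10) = 0.205.

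Simulation agrees. With separate series the SD falls to about 0.03 to 0.04 at N = 50, and to about 0.07 to 0.12 at N = 20.

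**Effect on the estimate.** A hospital difference of D shifts the estimate by D times the difference in share. For D = 1 at N = 50, one SD is 0.14 point and two SDs are 0.28 point, which is 14% of the 2-point design effect.

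**Share of the variance, 50:50 split.**
- Variance of the unadjusted estimate: 2 × 2.5²/25 = 0.50 (standard error 0.71).
- Part due to hospital mix: D² × 0.25 × 2/25 = 0.02 × D².
- D = 0.5: 0.005/0.50 = 1%. D = 1: 0.02/0.50 = 4%. D = 2: 0.08/0.50 = 16%.

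**Effect on power at D = 1.** Take the SD of 2.5 to include the hospital difference. The within-hospital SD is then sqrt(6.25 − 0.25) = 2.45 and the effect size is 2/2.45 = 0.816. Two-sided power at 25 per group rises from 79.1% to 80.7%.

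**The case against.** The strongest reply is that the loss is small and partly hypothetical. Nothing in the protocol shows that the two hospitals differ in pain outcome. They belong to one institution, the embolization is to be identical for both arms, and recovery nurses follow a specified escalation regimen. The plan never says that there is only one envelope series. The hospital–initials–envelope-number ID code fits either arrangement, and the login example in Appendix III (R001) does not settle it. All of this stands, and it is why the point is minor. The silence on the number of series is nevertheless a gap that the plan should close.

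A reader might infer three stronger things that the documents do not support.

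- **That the interval of up to three months breaks the blocks over time, or that cancelled patients leave unused allocations.** The interval runs from the consultation to the procedure. Section 7.1, Table 1 and section 7.4 randomize on the procedure day, and Appendices I and II attach and open the envelope only at the block. A patient who cancels earlier has used no envelope. Even if numbers were fixed at consultation, most balance over time would survive. With accrual of 1 to 4 patients a month and delays uniform over 0 to 3 months (both assumed), the 95th percentile of the largest running arm difference is 3 to 5 patients. It is 2 to 3 in procedure-day order and 15 to 16 under simple randomization.
- **That the treatment estimate is biased.** Allocation does not depend on hospital, so any imbalance is due to chance. The unadjusted test already carries it in its standard error and remains valid.
- **That the blocks cannot balance the arms.** A shared series still balances them overall and over calendar time. Only assured balance within hospital is missing.

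**Conclusion.** The gap is real but minor. The plan states neither stratification by hospital nor a hospital term, and it leaves inclusion undefined. On the natural reading of one shared series, a given hospital is out of balance by 5 or more patients in about one trial in five, and the difference in hospital share has an SD of about 0.14 at 50 patients and about 0.2 at 20. What would be gained is precision: about 4% of the estimate's variance, or roughly 79% to 81% power, if the hospitals differ by 1 point. The gain is smaller if they differ less and reaches 16% of the variance at 2 points. These figures rest on the assumed single series, hospital split and hospital difference. If the envelopes are already separate for each hospital, the design part falls away, and what remains is to say so and to name the hospital term. This is a cheap improvement, not a threat to the validity of the comparison.

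**What to change.** - **Section 6.3, lists.** Generate a separate permuted-block list and numbered envelope set for each hospital, and for any center added later.
- **Section 6.3, order of use.** Replace order of inclusion with the next unopened envelope at that hospital, taken on the procedure day. This agrees with section 7.1, Table 1, section 7.4 and Appendices I and II.
- **Analysis (synopsis, sections 5 and 8).** Include hospital as a factor in the primary comparison. The ID code already records it.

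The cost is one rerun of the randomization program before the envelopes are made, a change of wording, and one degree of freedom. An incomplete block at each hospital may leave the totals off 25/25 by a patient or two; small blocks keep this down. If the envelopes already exist, the hospital factor alone can still be added.

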7.1. Study Design and procedures

This is a double-blinded prospective randomized clinical study. All procedures will be performed by experienced interventional radiologists in the two MUHC study centers: Royal Victoria Hospital and Montreal General Hospital. Other Canadian hospital centers have shown interest in this protocol and may be added to the study at later dates.

Upon referral to the angiography department for a UAE, the radiologist will assess the patient to determine if she is eligible for recruitment into the study based on the inclusion and exclusion criteria (see Appendix I). This will be performed at the time of a consultation, which occurs up to three months before the actual procedure. If the patient is eligible, she will be explained the study and provided with an information sheet. She will be allowed to decide immediately whether she wants to participate or will be allowed to think about it and left to decide on the day of the procedure. An informed consent will be signed. The visual analogue scale will be explained as well as the commitment to complete the data sheets and return them, or to use the web service.

On the day of the procedure, a randomization envelope will be opened and the person will be assigned to either the sham procedure group or to the SHGNB group.

For both groups the UAE procedure itself will be identical. During the UAE procedure the patient will be offered IV sedation at the start to the amount of 1 mg of midazolam and 50 ug of fentanyl. Further additional doses will be upon request from the patient only. The patient will be informed to ask for more if she needs it. Prior to giving another dose, the patient will be asked to rank their discomfort on a scale of 0-10.

The UAE procedure consists of embolization of both uterine arteries. The SHGNB is usually performed in between embolization of both sides. Therefore for the SHGNB group, the block will be performed after the left uterine artery has been embolized. Following the block, the right uterine artery will be embolized. Similarly the sham procedure will also be performed at the time between both embolization.

In order to preserve the blinding, the block will be performed by a qualified IRMD, not involved with the UAE. Therefore, after the left uterine artery has been embolized, the UAE operator and accompanying technologists will leave the room. The patients vision will be blocked via a sheet placed in between their eyes and the operating field so that they cannot see what procedure will be done. The second operator will come into the room and perform the sham procedure or the SHGNB based on patient assignment to either group and will then leave the room. The primary operator will then return to complete the UAE procedure.

The sham procedure will consist of depositing a small amount of contrast and anesthetic agent into the subcutaneous tissues of the infraumbilical region. As this procedure will be much faster, the block IRMD will be asked to take some extra time in the process to extend the time to a similar amount of time that is needed for the SHGNB.

In the case of the SHGNB, the infraumbilical region will be penetrated by the same size needle as the sham procedure but advanced deeper, past the subcutaneous tissues into the abdomen up to the spine. Once the target is reached, contrast will be injected to ensure that the tip is in the appropriate location and the anesthetic agent will be injected (0.75% ropivacaine).

For the sake of blinding, the patient will be told that the SHGNB and sham procedure can cause similar symptoms depending on the patient. Some patients feel the discomfort at the skin and others deeper. It is our experience that this is the case, with some patients undergoing SHGNB feeling only the skin puncture. In any case, it is also our experience that the pain felt by either a sham procedure or a SHGNB is very short lived and extremely well tolerated by the patients. By attributing similar symptoms to the sham procedure and telling the patient that some patients have no significant discomfort with the SHGNB other than the crossing of the skin we hope to blind the patient so that she does not know whether only the skin was frozen or whether they have had a SHGNB.

Subject data collection at the time of enrollment will include demographics, relevant medical history and vital signs. Subjects will be followed-up as outlined in Table 1 to assess adverse events related to the procedures and clinical success of the procedure. Individual data collection will be considered complete at the time of the follow-up consultation 4-6 months after the UAE procedure.

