accordingly. We expect that the data analysis will consist of regression analysis of the temporal pain level distribution between the group with and without the SHGNB. Continuous variable data, with normal distributions, subgroup analysis of the secondary objectives will be compared using a Student's t- test.

▪ **Sample size calculation**

Sample size calculations are based on published data showing the average pain felt by ladies post uterine artery embolization being of 7/10 with a standard deviation of approximately 2.5. The published study of SHGNB for UAE demonstrated a decrease in pain from 7 to 5-2 depending on the analgesics regimen used [6]. We opted for the conservative drop in pain scale from 7 to 5 with a standard deviation of 2.5. This gives an effect size of 0.8. With type I error (alpha) set at 0.05 and type II error (beta) set at 0.2 (power of 80%), the sample size calculations yields a needed sample size of 42. We expect up to a 20% drop out rate due to loss to follow-up, giving a total sample size needed of 50, leaving 25 patients per group. [8]

If the analysis of the data after recruiting 50 patients is highly suggestive of an effect but without statistical significance, and if the calculations suggest we could get statistical significance by doubling the number of participants, and there have been no significant adverse events from the nerve block, we would increase the number of patients to 100. If adverse events have occurred, the number would not be increased unless approval by the ethics committee.

▪ **Interim analysis**

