Data integrity will be maintained throughout the study. Logic rules within the database will be used to maximize integrity, and random data validation checks will be performed routinely. The research investigator will review studies and patients' data on a monthly basis to ensure that patient follow-up is proceeding as expected. All cases where the research investigator finds a discrepancy in imaging interpretation or outcome assessment will be reviewed by the Adjudication Committee, consisting of the principal investigators. An independent radiologist from the MUHC will be asked to determine the outcome of a dispute amongst the Adjudication Committee.

8. Data Analysis:

Data will be collected and tabulated using the commercially available JMP10/SAS statistical analysis software (SAS Institute Inc., Cary, NC, USA). Descriptive statistics will be provided for the efficacy outcome results and will be presented in terms of percentage, frequency, means and 95% confidence interval of the means. Differences between both groups will be compared using the Chi-square test for categorical variables and Student's t- test for the continuous variables. ANOVA test and multivariate logistic-regression analysis will be used to compare interplay of more than two variables. Two-tailed p-values of less than 0.05 will be set for statistical significance.

9. Ethical considerations:

Research Ethics approval from the MUHC Research Ethics Board office will be obtained prior to the commencement of the study or related research procedures. All patients will be informed about the data that will be gathered for the study. All patients will have the ability to refuse participating in the study as soon as they are able to evaluate it and give their approval or not. Patients will always be given options to ask questions at any time and questions will be answered in a non-intimidating way so as to try to avoid influencing the patient's decision. At any time, the patient can decide to remove himself from the study. If this is the case, he will receive the standard of care.

No unique patient identifying data will appear on the sheets that will be coded only by study identification number. A key linking the patient name and study identification number will be maintained in a separate database. All datasheets will be kept in a locked, dedicated research office. All computer records will be maintained in a

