Appendix II - At time of UAE

Identification code: _____

Date of UAE: _____ (YY/ MM / DD)

RVH/MGH # _____ Age: _____

Do not open envelope until ready to do block (i.e. when switch doctors)

Consent signed: Yes No (do not proceed)

UAE PROCEDURAL DETAILS (to be filled by UAE IR without knowledge of Randomization group):

Pain scale at start of procedure (0-10): _____ (time: __:__)

Embolization material and size used: _____

Arteries embolized:

	Rt UA	# vial of PVA: _____
	Lt UA	# vial of PVA: _____
	Rt OA	# vial of PVA: _____
	Lt OA	# vial of PVA: _____

Other: _____ # vial of PVA: _____

Total fluoroscopy time of entire procedure: _____

Ovarian artery anastamosis seen?

No
 Left
 Right

Complications during UAE:

Pain (scale 1-10: _____)
 Arterial spasm - artery: _____
 Extravasation - artery: _____
 Groin hematoma

Other: _____

How many sites of injections: 1 or 2 or >2

Immediate complications from SHGNB/SHAM procedure:

Pain - where: _____

Bleeding

Rigors/Fever

Other: _____

IR UAE: _____ IR SHGNB: _____

Technologist: _____

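### No pain score is scheduled between left-artery embolization and the block or sham, so an inexpensive pre-injection covariate is never collected

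*Combined protocol and SAP*

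**What the plan says.** **Sequence.** Section 1.2 describes the left artery being treated before the right. Section 7.1 places the superior hypogastric nerve block (SHGNB) between the two: "Therefore for the SHGNB group, the block will be performed after the left uterine artery has been embolized". The sham is given at the same point. The embolization operator leaves the room, a second operator gives the assigned injection, and the first returns to treat the right side.

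**Scheduled pain scores.**
- Appendix II: at the start of the procedure, before any embolization.
- Appendix III: on arrival in and departure from recovery.
- Section 5: immediately after the procedure, 2 hours after it, and just before discharge.
- Sections 5 and 7.5: home sheets up to day 10.

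**Items that come close.** On additional sedation, Section 7.1 says: "Prior to giving another dose, the patient will be asked to rank their discomfort on a scale of 0-10". Appendix II also has a pain scale among the complications during embolization, with no time attached.

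**Envelope.** Appendix II instructs: "Do not open envelope until ready to do block".

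**Analysis.** Section 5 expects a regression of pain over time by group. Section 8 adds t-tests, ANOVA and multivariate logistic regression. Neither names a baseline or pre-injection covariate.

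**The concern.** The interval between left embolization and the injection is the one moment when every woman has had an embolization and the assigned injection cannot yet have influenced her score. A rating taken then may say more about how she reacts to embolization than a rating taken before any artery is treated. As a covariate it could reduce the residual variance of the post-procedure scores. Tabulated by arm, it would show whether the groups were alike just before the injection.

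The existing items do not fill the gap. Under Section 7.1 the pre-dose rating exists only for women who ask for more sedation, and Appendix II has no field for it. The complication entry cannot be placed before or after the injection. A score not taken at that moment cannot be recovered later.

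Precision matters here because the trial is small and, under its own two-sided rule, has little power to spare.

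**Working it through.** **Inputs from the documents.** Section 5: "We opted for the conservative drop in pain scale from 7 to 5 with a standard deviation of 2.5" and "This gives an effect size of 0.8"; alpha 0.05; power 80%; 42 evaluable; 50 recruited, 25 per arm; up to 20% lost to follow-up. Section 8: "Two-tailed p-values of less than 0.05 will be set for statistical significance".

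**Assumption.** The correlation ρ between the left-artery score and the later pain score is not in the documents, so a range is shown.

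**1. The plan's own figure.** Effect size d = (7 − 5)/2.5 = 0.8. A two-sample t-test (noncentral t) at 80% power needs:
- one-sided 0.05: 21 per arm = 42, which matches the plan;
- two-sided 0.05: 26 per arm = 52, which does not.

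The recruited total follows as 42 × 1.2 = 50.4, stated as 50. Under the two-sided rule, 42 evaluable women (21 per arm) give 71.6% power.

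**2. Which denominator applies.** Section 5 attributes dropout to loss to follow-up. In-hospital scores are collected before discharge, so 25 per arm is the natural base for them. For home scores with the full 20% lost, 50 × 0.8 = 40, or 20 per arm.

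**3. Effect of adjustment.** With the score as a covariate:
- residual SD = 2.5 × √(1 − ρ²);
- adjusted effect size = 0.8/√(1 − ρ²);
- noncentrality = adjusted effect size × √(n/2), with n per arm;
- degrees of freedom = 2n − 3 (2n − 2 unadjusted).

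Example, ρ = 0.4 and n = 25: √(1 − 0.16) = 0.917; adjusted effect size 0.8/0.917 = 0.873; noncentrality 0.873 × √12.5 = 3.09; 47 degrees of freedom; power 85.6%.

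| ρ | Confidence interval width, relative | Power, 25 per arm | Power, 20 per arm |
|---|---|---|---|
| unadjusted | 1.00 | 79.1% | 69.3% |
| 0.1 | 0.995 | 79.5% | 69.7% |
| 0.2 | 0.98 | 80.7% | 71.0% |
| 0.3 | 0.954 | 82.7% | 73.3% |
| 0.4 | 0.917 | 85.6% | 76.7% |
| 0.5 | 0.866 | 89.2% | 81.2% |
| 0.6 | 0.80 | 93.4% | 86.8% |

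**4. Gain over the start score.** The start score is already collected, so the fair comparison is with adjusting for it. Let r0 and r1 be the correlations of the start and left-artery scores with the outcome, and r01 the correlation between them (all assumed). Then R² = (r0² + r1² − 2·r0·r1·r01)/(1 − r01²), and the further cut in residual variance is 1 − (1 − R²)/(1 − r0²).
- r0 = 0.2, r1 = 0.5, r01 = 0.3: R² = 0.23/0.91 = 0.253; further cut 22%.
- r0 = 0.3, r1 = 0.3, r01 = 0.5: R² = 0.09/0.75 = 0.12; further cut 3%.

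The added value therefore ranges from useful to negligible.

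**The case against.** **Randomization already protects the comparison.** This stands. A reader might infer that the missing score biases the result, or that left-sided pain sits in the outcome as a component the block cannot touch. The documents support neither. The synopsis rationale describes the plexus as relaying pain from the uterus, so continuing left-sided pain is itself something the block is meant to relieve. Only the value of the earlier score is fixed before the injection.

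**The gain is speculative.** This stands in part. The score would follow one artery only, under midazolam and fentanyl, while Section 1.3 puts peak pain about 2 hours after the procedure. The correlation could be low. The calculation also uses a single time point, whereas Section 5 expects a regression over time and names no primary time point.

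**For in-hospital scores power is already near target.** This stands: 79% with 25 per arm. The 69% figure applies only where the full 20% is lost.

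**Some pre-injection ratings may exist anyway.** Section 7.1 gives extra sedation only on request, while the synopsis describes intravenous analgesia offered on a fixed schedule. The passages conflict and must be reconciled, because the answer decides how often the pre-dose rating is taken. Under either reading the rating has no field on Appendix II and is not tied to the moment before the injection.

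**The score may not precede allocation.** Appendix II holds the envelope until the operators switch; Section 7.4 has it opened once the woman agrees to take part, with the embolization then proceeding; Section 7.1 says only that it is opened that day. Even with early opening, a score asked by the blinded operator of a blinded patient still precedes the injection and remains a valid covariate.

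**Conclusion.** The point holds as a missed opportunity, not a flaw in validity. No pain score is systematically scheduled between left embolization and the injection, and no existing item substitutes for one. What is forgone is some precision and a comparability check just before the injection.

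Over assumed correlations of 0.1 to 0.6, power rises from 79% to between 79.5% and 93% with 25 per arm, and from 69% to between 70% and 87% with 20 per arm. Below about 0.3 the gain is under 4 percentage points in either case. These figures rest on the plan's 2-point difference and SD of 2.5, a two-sided 0.05 test, one time point and a linear covariate.

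A reader might also infer that this score would make good the gap between 42 and the 52 needed under two-sided testing. The documents do not support that. With 42 evaluable women power is 78.8% at a correlation of 0.4 and 83.1% at 0.5, so 80% is regained only if the correlation is a little above 0.4, and nothing in the documents shows that it is.

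**What to change.** 1. Add one timed line to Appendix II: *Pain 0-10 after left uterine artery embolization, before operator switch and before the envelope is opened*. The blinded embolization operator asks it of every woman.
2. Prespecify this score, together with the start-of-procedure score already collected, as a covariate in the Section 5 regression of post-procedure pain.
3. Tabulate the score by arm as a description of comparability just before the injection.
4. Reconcile the envelope-opening time in Sections 7.1 and 7.4 with Appendix II.
5. Reconcile the synopsis and Section 7.1 on when intravenous analgesia is offered during the procedure.

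The cost is one question during the procedure, one form line and one degree of freedom for the new covariate. No visit, staff or patients are added. The downside is little return if the correlation proves low.
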